#### 11.2.15 Laboratory Data (Safety labs)

This dataset contains data extracted from the Laboratory Test Findings (LB) Domain and its supplemental domain, excluding biomarkers and previous testings for Anti-Double Stranded DNA and Antinuclear Antibodies, in a basic data structure.

To facilitate the reporting, parameter category (numeric and character) are defined based on the Category and Method:

| Parameter Category (N) | Parameter Category                | Source  |
|------------------------|-----------------------------------|---|
| 1                      | HEMATOLOGY                        | HEMATOLOGY                                      |
| 2                      | CLINICAL CHEMISTRY                | CHEMISTRY                                       |
| 3                      | COAGULATION TESTS                 | COAGULATION                                     |
| 4                      | VIRUS SEROLOGY                    | IMMUNOLOGY                                      |
| 6                      | URINALYSIS, DIPSTICK              | Category = 'URINALYSIS' and Method = 'DIPSTICK' |
| 7                      | URINE PROTEIN-TO-CREATININE RATIO | Category = 'URINALYSIS'                         |
| 8                      | TEST FOR TUBERCULOSIS             | IMMUNOLOGY                                      |
| 9                      | PREGNANCY TEST                    | CHEMISTRY                                       |
| 9                      | PREGNANCY TEST                    | URINALYSIS                                      |

Some parameters being assayed in the serum and in the urine (assay and dipstick), parameters need to be renamed depending on Category, Method and Specimen Type:

The parameter code (no longer than 8 characters) corresponds to:

- the Test Code for Category equal to ‘CHEMISTRY’, ‘COAGULATION’ and ‘HEMATOLOGY’,
- the concatenation of ‘U’ and the Test Code for Category equal to ‘URINALYSIS’,
- the concatenation of ‘UD’ and the Test Code for Category equal to ‘URINALYSIS’ and Method equal to ‘DIPSTICK’.

The parameter corresponds to the concatenation of:

- the Category,
- the Lab Test or Examination Name,
- the Standard Units in brackets.

For the parameters assayed as a continuous variable, **Baseline**, **Absolute value at each post-baseline assessment**, **Absolute and percent change from baseline to each post-baseline assessment** variables are populated as described in the general section.

For the parameters assayed as a categorical variable (e.g., Protein), the analysis value is defined only as a character value.

**Analysis Reference Range Indicator** is derived to identify marked abnormalities according the Adapted table 5 from the study protocol [included in Section 15]. It is only defined for results coming from the central laboratory, it is based on the normal range indicator provided by ACM (L, LL, H, HH) and augmented or modified according to the adapted table 5.

#### 11.2.16 Exploratory biomarker data

This dataset contains the following parameters, assayed by the central laboratory, except for Blood lymphocyte subsets, from the LB Domain, mapped into a basic data structure.

**Baseline** is defined as the last non-missing value (numeric result in standard units) before date and time of first dose intake of double-blind treatment. Values below the lower limit of quantification (for example: LLQ = 2) recorded as “< LLQ” are set to half that limit (i.e., LLQ/2). Values recorded above or equal the upper limit of quantification are set to the upper limit. No imputation is performed for values recorded greater than the ULQ.

**Baseline value in categories** is defined from numeric and character results in standard units using the categorization depicted in the corresponding sections.

**Analysis value** is defined as the value at the visit (numeric result in standard units). Values below the lower limit of quantification (for example: LLQ = 2) recorded as “<

LLQ" are set to half that limit (i.e., LLQ/2). Values recorded above or equal the upper limit of quantification are set to the upper limit. No imputation is performed for values recorded greater than the ULQ.

**Analysis value in categories** is defined from numeric and character results in standard units using the categorization depicted in the corresponding sections.

**Absolute and percent change from baseline to each post-baseline assessment** variables are populated as described in the general section.

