#### 4.3.3 Exploratory biomarkers variables

For exploratory biomarkers such as ANA titers or C-reactive protein (CRP), the planned analyses encompass the description of the values as a continuous variable (absolute value, absolute change from baseline and percent change from baseline). A selection of these biomarkers will be summarized as categorical variables.

*Rationale for change:* During the conduct of the study, it was realized that, for some biomarkers (ANA titers, CRP, anti-ribosomal P), more than one-third of the values are either recorded below the lower limit of quantification ('<1'; BLQ) or above upper limit of quantification ('>100'; ULQ). Considering this, descriptive results may be biased when the total number of BLQ and ULQ values is large; in these circumstances, the variables are described only as categorical variables.

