#### 5.7.3.2 *Exploratory biomarker variables*

- ANA, anti-dsDNA, complement factors and exploratory biomarkers

The following parameters are assayed by the central laboratory:

- ANA, anti-dsDNA, complement C3 and C4 (all visits except Visit 3);
- IgM, IgG, IgA, CRP, fibrinogen, and B lymphocyte stimulator (BLyS) (Visit 2 and Visits 4 to 7).

The following parameter is assayed by Translational Science Biology:

- C-X-C motif chemokine ligand 10 (CXCL10) (EDTA-plasma; Visit 2 and Visits 4 to 7).

The following endpoints are defined:

- Change in immunoglobulin serum levels (IgG, IgM, IgA) from baseline to each post-baseline analysis visit;
- Change in ANA and anti-dsDNA antibody titers from baseline to each post-baseline analysis visit;
- Change in serum complement components C3 and C4, CRP, fibrinogen, BLyS and CXCL10 from baseline to each post-baseline analysis visit.

If the number of values recorded as below or above the limit of quantification is more than one third overall, the parameter is only described as a categorical variable (value at each analysis visit).

Categories are defined using the reference ranges and the reportable ranges provided by the central laboratory.

**Table 5** Exploratory biomarker variables evaluated during the study

| Parameter (unit)          | Reference Ranges | Reportable Ranges | Categorization   |
|---------------------------|------------------|-------------------|--|
| ANA titer                 | < 40             | <40; >=640        | < 40, 40, 80, 160, 320, >=640                            |
| anti-dsDNA (U/mL)         | < 100            | 50; 1000          | < 1.0, 1.0 - 99.9, >= 100                                |
| Complement C3 (g/L)       | 0.9 ; 1.8        | 0.50; 1125.00     | < 0.90, 0.90 - 1.80, > 1.80                              |
| Complement C4 (g/L)       | 0.18 ; 0.45      | 0.40; 700.00      | < 0.05, 0.05 - 0.17, 0.18 - 0.45, > 0.45                 |
| C Reactive Protein (mg/L) | < 8.00           | 4.00; 999.00      | < 4.00, 4.00 - 7.99 , >= 8.00                            |
| Fibrinogen (g/L)          | 2.1 ; 4.7        | 0.01; 7.0         | < 0.5, 0.5 - 1.0, 1.1 - 2.0, 2.1 - 4.7, 4.8 - 5.9, > 5.9 |
| Immunoglobulin A (g/L)    | 0.4 ; 3.5        | 0.15; 54.00       | < 0.4, 0.4 -3.5, > 3.5                                   |
| Immunoglobulin G (g/L)    | 6.5 ; 16         | 0.70; 340.00      | < 6.5, 6.5-16.0, >16.0                                   |

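### SAP 11.2.16 gives two incompatible instructions for exploratory biomarker results above the upper limit of quantification, and under one of them such results leave the continuous summaries

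*SAP*

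**What the plan says.** SAP 11.2.16 derives the exploratory biomarker variables. For the baseline value and again for the analysis value it states, in two consecutive sentences, that results at or above the upper limit of quantification (ULQ) "are set to the upper limit. No imputation is performed for values recorded greater than the ULQ". Results below the lower limit (LLQ) are set to half that limit. The analysis value "is defined as the value at the visit (numeric result in standard units"), whereas categories may be formed from numeric and character results.

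SAP 4.3.3 shows how out-of-range results are recorded, including those "or above upper limit of quantification ('>100'; ULQ"). It also gives the reason for a categorical fallback: "descriptive results may be biased when the total number of BLQ and ULQ values is large". SAP 5.7.3.2 sets the trigger: "If the number of values recorded as below or above the limit of quantification is more than one third overall", the marker is described by categories only. The markers that SAP 4.3.3 names as over that threshold are ANA, CRP and anti-ribosomal P.

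SAP 10.8.1.2 plans descriptive summaries of absolute values, absolute changes and percent changes by visit and group, with geometric means. The only worked conversion of an upper-limit result is the ANA table in SAP 11.2.16.2, where '>=640' becomes 640.

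**The concern.** The first sentence covers everything at or above the limit and the second covers everything above it. A result above the limit therefore falls under both. Two programmers could build different datasets and each could claim to follow the SAP.

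The choice is not neutral. Leaving a '>4000' record un-imputed removes it from a variable that must be numeric, while a result below the lower limit always stays in. Only the upper tail is lost. For anti-dsDNA and BLyS that tail is the most abnormal end of the scale, and neither marker is among those named as switching to categories.

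The loss can also turn into a substitution. Baseline is the last non-missing pre-dose value, and anti-dsDNA is measured at both Screening and Day 1, so an un-imputed Day 1 result could be replaced by an in-range Screening result. Likewise, the end-of-treatment record in SAP 11.1.1 takes the latest non-missing value, so an un-imputed Week 12 result could be replaced by an earlier in-range one.

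**Working it through.** **Inputs from the documents.**
- BLyS: reportable range 63 to 4000 pg/mL, reference range 584 to 1186, top category '>4000' (SAP Table 5).
- Anti-dsDNA: reportable range 50 to 1000 U/mL (SAP Table 5). Treating 1000 as the ULQ is an inference, because no '>1000' result or category appears.
- Group sizes: 12 per dose and 16 on placebo (Protocol 11.6.1).

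No planned figure depends on this rule, so there is none to reproduce.

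**One record, two rules.** Take a BLyS result recorded as '>4000'. Under the first sentence the analysis value is 4000. Under the second it stays a string, and the numeric analysis value is missing. The ANA conversions ('<40' to 20 = 40/2, and '>=640' to 640) agree with the lower-limit rule and with the first sentence.

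**Effect on a visit mean.** Let k of n values lie above the ULQ and let m be the mean of the others.
- Set to ULQ: ((n − k)m + k·ULQ)/n
- Left out: m
- Difference: (k/n)(ULQ − m), positive whenever m is below the ULQ

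With n = 12 and k = 1 (k and m are assumed; the documents give neither):

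| Marker | m | Set to ULQ | Left out | Relative difference |
|---|---|---|---|---|
| BLyS | 800 | 1066.7 | 800 | −25.0% |
| BLyS | 1186 | 1420.5 | 1186 | −16.5% |
| BLyS | 2000 | 2166.7 | 2000 | −7.7% |
| Anti-dsDNA | 100 | 175.0 | 100 | −42.9% |
| Anti-dsDNA | 200 | 266.7 | 200 | −25.0% |
| Anti-dsDNA | 400 | 450.0 | 400 | −11.1% |

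For example, (11 × 1186 + 4000)/12 = 1420.5, and 1420.5 − 1186 = 234.5 = (4000 − 1186)/12.

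**Both rules against the true mean.** Assume a lognormal marker with log SD 1.2, ULQ 1000 and 10% of values above it. The true mean is 441. Setting to the ULQ gives 335 and leaving out gives 261. Both are low: the first by 106, and the second by a further 74. With log SD 1.0 and 10% above, the geometric mean is 0.95 of the true value when set to the ULQ and 0.82 when left out.

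**Change from baseline.** Assume log SD 1.0, correlation 0.8 and 10% of baselines above 1000, with any subject dropped if either value exceeds the limit. The error is towards zero under both rules.

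| Ratio of follow-up to baseline level | True mean change | Set to ULQ | Left out | Subjects losing their change |
|---|---|---|---|---|
| 0.5 | −228.9 | −164.4 | −140.0 | 10.4% |
| 0.7 | −137.3 | −92.4 | −78.8 | 11.5% |
| 1.3 | +137.4 | +76.6 | +65.4 | 18.3% |

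**The case against.** The sentences might be reconciled in three ways. The second could mean only that nothing beyond the limit is extrapolated once the value is set to it; then nothing is lost. It could apply to records written '>ULQ' and the first to records written '>=ULQ'; the ANA row fits that too, but '>4000' would still drop out. Or it could mean that numeric results above the limit are kept as measured; then a measured value stays above the limit while a '>' record that may be higher does not. The text states none of these. That other readings exist supports clarifying the wording. It does not establish that data will be lost.

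A reader might go further and infer that the highest anti-dsDNA and BLyS values will drop out and bias the group means low. The documents do not support that as a fact. They give no count of over-limit results for either marker, and the count could be zero. A scenario with 30% of anti-dsDNA values above the limit has no support either: positive anti-dsDNA is not an entry requirement, and the one-third trigger counts results below and above the limits together.

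Nor does a patient with one over-limit result disappear. In-range results still enter their own visit summaries, all results are listed, and any categorical table keeps the character result. SAP 4.3.3 promises such tables only for a selection of markers, however, and the top anti-dsDNA category starts at 100, so it would not show movement near 1000.

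Finally, setting to the limit is itself biased, and it is not always closer to the truth for change. With 30% of baselines above the limit, a 30% reduction, and between- and within-subject log SDs of 1.2 and 0.3, the mean change is about −95 when set to the ULQ and −97 when left out, against a true value near −338. This stands. The case for the rule is that it is single, reproducible and keeps the subjects, not that it is unbiased.

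**Conclusion.** The contradiction is real and appears in both the baseline and the analysis-value definitions. Following the second sentence removes '>ULQ' string results from the continuous summary of that visit, and loses or mis-sources the change from baseline, while low results are retained. The mean of absolute values is then lower than under the first sentence by (k/n)(ULQ − m). In a group of 12 with a single such result, that is about 8% to 25% for BLyS and 11% to 43% for anti-dsDNA over the assumed values of m. The actual size is unknown.

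The conclusion rests on over-limit results arriving as strings, as SAP 4.3.3 illustrates, and for anti-dsDNA on 1000 being the operative limit. It concerns exploratory descriptive summaries only; the lymphocyte-count analysis is untouched. This is a minor point, worth correcting because the correction is nearly free.

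**What to change.** In SAP 11.2.16, under both the baseline and the analysis value, keep one rule: results recorded as at or above the ULQ are set to the ULQ, as the ANA table already does for '>=640'. Delete the sentence stating that results above the ULQ are not imputed. Beside each continuous summary, report the number of values at the ULQ by visit and group, with a note that means and changes are understated when that number is not small.

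The cost is one sentence deleted in two places and one added count. No new data are needed, and it can be done before database lock. The price is that movement above the limit is invisible and that any numeric result the laboratory reported above the limit would be overwritten. The documents show no such results; the laboratory's reporting convention should be checked before the wording is fixed.

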#### **11.2.16.1 Baseline disease characteristics, Exploratory disease biomarker**

The following parameters are assayed by the central laboratory at Visit 2 only: anti-Smith, anti-cardiolipin (IgA, IgG, IgM), anti-ribosomal P.

#### **11.2.16.2 Exploratory biomarker variables**

The following parameters are assayed by the central laboratory:

- ANA, anti-dsDNA, complement C3 and C4 (all visits except Visit 3);
- IgM, IgG, IgA, CRP, fibrinogen, and BLyS (Visit 2 and Visits 4 to 7);

The following parameters are assayed by Translational Science Biology at Actelion:

- CXCL10 (EDTA-plasma; Visit 2 and Visits 4 to 7).

For the antinuclear antibody (ANA) test, 2 results (2 records) are provided by the central laboratory, only one observation is kept:

| Character Result
in Std Format for
Antinuclear Antibodies | Character Result
in Std Format for
Antinuclear Antibodies Titer | Analysis
Value | Analysis
Category 1 | Analysis
Category 2 |
|---|---|-------------------|------------------------|------------------------|
| NEGATIVE*   | NOT APPLICABLE
(Vendor Name = ACM EUROPE)                          | 20                | NEGATIVE               | < 40                   |
| NEGATIVE*   | <40
(Vendor Name = ACM US)   | 20                | NEGATIVE               | < 40                   |
| POSITIVE  | 40  | 40                | POSITIVE               | 40                     |
| POSITIVE  | 80  | 80                | POSITIVE               | 80                     |
| POSITIVE  | 160   | 160               | POSITIVE               | 160                    |
| POSITIVE  | 320   | 320               | POSITIVE               | 320                    |
| POSITIVE  | >=640   | 640               | POSITIVE               | >= 640                 |

\* In case the qualitative test for ANA is negative, ACM US reports '<40' and ACM Europe 'Not applicable' for the titer result.

For the other analysis parameters, **Baseline, Absolute value at each post-baseline assessment, Absolute and Percent change from baseline to each post-baseline assessment** variables are populated as described in the general section.

- Blood lymphocyte subsets

The list of parameters assayed by Translational Science Biology at Actelion is provided below:

**Table 14 Lymphocyte subsets: parameters and units**

| Category   | Specimen Type | Lab Test                                  | Lab Test Code | Original Units | Conventional Units | Standard Units     |
|------------|---------------|---|---------------|----------------|--------------------|--------------------|
| CHEMISTRY  | Plasma        | CXCL10                                    | CXCL10        | pg/mL          | pg/mL              | ng/L               |
| HEMATOLOGY | Blood         | B cells                                   | BCE           | cells/µL       | 10  µL | 10  /L |
| HEMATOLOGY | Blood         | Naïve B cells                             | NAIVBCE       | cells/µL       | 10  µL | 10  /L |
| HEMATOLOGY | Blood         | Pre-germinal center B cells               | PRGCBCE       | cells/µL       | 10  µL | 10  /L |
| HEMATOLOGY | Blood         | Post-germinal center memory B cells       | PSGCMBCE      | cells/µL       | 10  µL | 10  /L |
| HEMATOLOGY | Blood         | Double-negative B cells                   | DNEGBC        | cells/µL       | 10  µL | 10  /L |
| HEMATOLOGY | Blood         | Classical (Chain switched) memory B cells | CSMEMBCE      | cells/µL       | 10  µL | 10  /L |
| HEMATOLOGY | Blood         | IgD+ memory B cells                       | IGDMBCE       | cells/µL       | 10  µL | 10  /L |
| HEMATOLOGY | Blood         | CD20-/CD38+ B cells                       | CD20_38BC     | cells/µL       | 10  µL | 10  /L |
| HEMATOLOGY | Blood         | Plasma cells                              | PLSMCE        | cells/µL       | 10  µL | 10  /L |
| HEMATOLOGY | Blood         | CXCR3+ B cells                            | CXCR3         | cells/µL       | 10  µL | 10  /L |
| HEMATOLOGY | Blood         | Transitional B cells                      | TRANBCE       | cells/µL       | 10  µL | 10  /L |
| HEMATOLOGY | Blood         | Plasmablast-like cells                    | PLSPCE        | cells/µL       | 10  µL | 10  /L |
| HEMATOLOGY | Blood         | T cells                                   | TCE           | cells/µL       | 10  µL | 10  /L |

| Category   | Specimen Type | Lab Test                      | Lab Test Code | Original Units | Conventional Units | Standard Units |
|------------|---------------|-------------------------------|---------------|----------------|--------------------|----------------|
| HEMATOLOGY | Blood         | T helper (Th)                 | TH            | cells/µL       | 10^3 µL            | 10^9/L         |
| HEMATOLOGY | Blood         | Th central memory (CM)        | TH_CM         | cells/µL       | 10^3 µL            | 10^9/L         |
| HEMATOLOGY | Blood         | Th naïve                      | TH_N          | cells/µL       | 10^3 µL            | 10^9/L         |
| HEMATOLOGY | Blood         | Th effector memory (EM)       | TH_EM         | cells/µL       | 10^3 µL            | 10^9/L         |
| HEMATOLOGY | Blood         | Th EM RA+ (EMRA)              | TH_EMRA       | cells/µL       | 10^3 µL            | 10^9/L         |
| HEMATOLOGY | Blood         | T regulatory (Treg)           | TREG          | cells/µL       | 10^3 µL            | 10^9/L         |
| HEMATOLOGY | Blood         | Double negative T cells (DNT) | DNEGTCE       | cells/µL       | 10^3 µL            | 10^9/L         |
| HEMATOLOGY | Blood         | T cytotoxic (Tc)              | TCE_CYTOX     | cells/µL       | 10^3 µL            | 10^9/L         |
| HEMATOLOGY | Blood         | Tc CM                         | TCCM          | cells/µL       | 10^3 µL            | 10^9/L         |
| HEMATOLOGY | Blood         | Tc naïve                      | NAIVTCE       | cells/µL       | 10^3 µL            | 10^9/L         |
| HEMATOLOGY | Blood         | Tc EM                         | TCE_EM        | cells/µL       | 10^3 µL            | 10^9/L         |
| HEMATOLOGY | Blood         | Tc EMRA                       | TCE_EMRA      | cells/µL       | 10^3 µL            | 10^9/L         |
| HEMATOLOGY | Blood         | Th follicular (Tfh)           | TH_F          | cells/µL       | 10^3 µL            | 10^9/L         |
| HEMATOLOGY | Blood         | Th1                           | TH1           | cells/µL       | 10^3 µL            | 10^9/L         |
| HEMATOLOGY | Blood         | Th2                           | TH2           | cells/µL       | 10^3 µL            | 10^9/L         |
| HEMATOLOGY | Blood         | Th17                          | TH17          | cells/µL       | 10^3 µL            | 10^9/L         |
| HEMATOLOGY | Blood         | Th1/Th17                      | TH1TH17       | cells/µL       | 10^3 µL            | 10^9/L         |
| HEMATOLOGY | Blood         | Tc CXCR5+                     | CXCR5         | cells/µL       | 10^3 µL            | 10^9/L         |
| HEMATOLOGY | Blood         | Tc CXCR3+                     | CXCR3         | cells/µL       | 10^3 µL            | 10^9/L         |

**Analysis value** is defined as the value at the visit (numeric result in standard units). Original results recorded as below the lower limit of quantification (LLOQ) are set to half of the LLOQ value.

**Baseline, Absolute value at each post-baseline assessment, Absolute and Percent change from baseline to each post-baseline assessment** variables are populated as described in the general section.

